### 1) Outcomes: (*Table 1*)

No.	Outcome Name	score	Criteria	type	Methods of aggregation
1ry	Salivary S.mutans count	VL: very low	10  cfu/ml	Categorical ordinal	Absolute risk will be reported for each intervention independently. Relative risk will be used to compare both interventions with 95 % CI.
		L: low	10  cfu/ml		
M: Moderate	10  cfu/ml				
H: High	10  cfu/ml				
2ry	Interdental plaque Bacterial count	Swapnil et al, 2018			
3ry	Salivary ph	Numerical values	Normal salivary ph = 6.2 - 7.6	Continous	Mean and Standard deviation
		Baliga et al, 2013			

## 2) Participant timeline: (Table 2)

Activity	Staff member	T0 Baseline	T1 After 5 min	T2 After 15 days
Recruitment	Y.S.	X		
Diagnosis	Y.S.	X		
Consent	Y.S.	X		
Baseline data collection	Y.S.	X		
Randomization	Y.S.	X		
Saliva & Plaque sampling	M.A.	X	X	X
Outcome assessment	H.M. E.M.	X	X	X

## 3) Sample size calculation:

A power analysis was designed to have adequate power to apply statistical test of the research hypothesis that dissolving xylitol chewing tablets will have the better antibacterial effect than xylitol chewing gum against mutans streptococci after 1 month. According to the results of *Swapnil et al. in 2018* in which the probability of bacterial count reduction to  $10^2$  for xylitol chewing gum (comparator) was (0.15), probability of bacterial count reduction to  $10^3$  was (0.6) and probability of bacterial count reduction to  $10^4$  was (0.25) with effect size  $w=0.578$  ( $n=29$ ). If the estimated probability of dissolving xylitol chewing tablets for bacterial count reduction to  $10^2$  is (0.35), probability of bacterial count reduction to  $10^3$  is (0.5) and probability of bacterial count

reduction to  $10^4$  was (0.15) with effect size  $w=0.43$  ( $n=53$ ). By adopting an alpha ( $\alpha$ ) level of 0.05 (5%), power=80%. The predicted sample size ( $n$ ) was a total of (82). Sample size was increased by (20%) to account for possible dropouts during follow-up intervals to be total of (98) cases i.e. (49) for each group. Sample size calculation was performed using G\*Power 3.1.9.2.

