## 2) Trial design:

Randomized clinical Trial, parallel arms.

Trial framework: Equivalence frame

Allocation ratio: 1:1.

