### **3) Statistical methods:**

Data will be analyzed using IBM SPSS advanced statistics (Statistical Package for Social Sciences), version 25 (SPSS Inc., Chicago, IL). Categorical data will be described as absolute risk for each intervention independently and relative risk when comparing both interventions. Comparisons between categorical variables will be performed using the chi square test and Kruskal Wallis will be used to test interaction of variables. Continuous data will be described using mean and standard deviation. Comparison between continuous data will be performed using t-test and two-way ANOVA will be used to test interaction of variables. A p-value less than or equal to 0.05 will be considered statistically significant and all tests will be two tailed.

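### The total of 82 adds two one-arm sample sizes (29 + 53); the tablet-versus-gum chi-square has about 48% power at 82 and 55% at 98, not 80%

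*Protocol*

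**What the plan says.** The Protocol, III.A 3) Sample size calculation, names the hypothesis to be powered as a between-arm one: "dissolving xylitol chewing tablets will have the better antibacterial effect than xylitol chewing gum against mutans streptococci after 1 month". It assumes these proportions reaching each salivary *S. mutans* count category:

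| | 10^2 | 10^3 | 10^4 | stated w | stated n |
|---|---|---|---|---|---|
| Gum | 0.15 | 0.60 | 0.25 | 0.578 | 29 |
| Tablets | 0.35 | 0.50 | 0.15 | 0.43 | 53 |

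The error rate and power are given as "level of 0.05 (5%), power=80" per cent, and the section concludes "The predicted sample size ( $n$ ) was a total of (82"). This is raised by 20% to 98, or 49 per group.

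For the analysis, III.C 3) Statistical methods says "Comparisons between categorical variables will be performed using the chi square test", and adds "A p-value less than or equal to 0.05 will be considered statistically significant and all tests will be two tailed". Table 1 (III.A 1) Outcomes) classes the primary outcome as ordinal and says "Relative risk will be used to compare both interventions with 95 % CI". Trial design gives 1:1 allocation and states "Trial framework: Equivalence frame".

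**The concern.** A two-arm comparison has one effect size, which measures how far the arms differ, and one total sample size. The Protocol gives no such effect size. It gives each arm its own w and its own n and adds the two. The gum arm has the larger w although tablets are expected to do better, which already suggests that neither w measures tablets against gum.

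If so, the 80% does not belong to the test the trial will run, and it is the only justification given for enrolling 98 patients. With the real power near one half, a non-significant result would say little. It could easily be misread as showing that the two products have the same effect, which is how the null hypothesis in section 2.2 is worded.

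**Working it through.** **Inputs.** The proportions, alpha of 0.05 and 80% power come from the sample size section. The chi-square test and two-sidedness come from Statistical methods, and 1:1 allocation from Trial design. The three proportions sum to 1 in each arm, so the fourth category in Table 1 (10^5) has no assumed probability. Both the one-arm and the between-arm tests therefore have 2 degrees of freedom. Power is taken from the non-central chi-square distribution with non-centrality N × w². For 80% power at alpha 0.05 and 2 df, the non-centrality must reach 9.635.

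**Step 1: reproduce 82.** Test each arm alone against equal thirds, with w² = Σ (p − 1/3)² / (1/3).

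- Gum: 3 × (0.03361 + 0.07111 + 0.00694) = 0.335, so w = 0.579. Then n = 9.635 / 0.335 = 28.8, rounded up to **29**.
- Tablets: 3 × (0.00028 + 0.02778 + 0.03361) = 0.185, so w = 0.430. Then n = 9.635 / 0.185 = 52.1, rounded up to **53**.
- Sum: 29 + 53 = **82**.

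Both effect sizes match (the Protocol truncates 0.5788 to 0.578), as do both n. Other readings do not match:

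- With 1 df the sizes are 24 and 43; with 3 df they are 33 and 59.
- Tablets against the gum proportions as a fixed null give w = 0.569 and n = 30. Gum against the tablet proportions gives w = 0.448 and n = 48.
- Equal quarters over the four categories of Table 1 give w = 0.883 and 0.762.

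**Step 2: the comparison the trial will make.** With 1:1 allocation the pooled proportions are (0.25, 0.55, 0.20). Each arm deviates from them by 0.10, 0.05 and 0.05 in absolute value.

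w² = 0.0100/0.25 + 0.0025/0.55 + 0.0025/0.20 = 0.0400 + 0.0045 + 0.0125 = 0.0570, so **w = 0.239**.

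For 80% power, w would have to be √(9.635/82) = 0.343 at 82, or √(9.635/98) = 0.314 at 98.

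| Evaluable patients | Non-centrality | Power |
|---|---|---|
| 82 | 4.68 | 47.6% |
| 98 (no loss) | 5.59 | 55.2% |
| 78 (98 less 20%) | 4.45 | 45.6% |
| 170 (85 per arm) | 9.70 | 80.3% |

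The minimum is 9.635 / 0.0570 = 169, or 170 for equal arms. Simulated trials agree: about 48% at 41 per arm, 56% at 49 per arm and 82% at 85 per arm.

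**Step 3: would another test rescue it?** Power on the same proportions:

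| Test | 82 | 98 |
|---|---|---|
| Wilcoxon rank test, tie-corrected, two-sided | 54% | 62% |
| Relative risk for 10^2 (0.35 v 0.15), 95% CI excluding 1 | 51% | 61% |
| Two-proportion test for 10^2, two-sided | 55% | 63% |
| Wilcoxon, one-sided | 67% | 73% |
| Two-proportion test for 10^2, one-sided | 68% | 75% |

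None reaches 80%, and the one-sided versions are excluded by the Protocol's two-tailed rule. Table 1 does not say how the relative risk splits the categories, so the cut at 10^2 is an assumption.

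**The case against.** **The null is inferred.** The Protocol never mentions equal thirds. That is true, although a match on two effect sizes and two sample sizes leaves little doubt. More importantly, the shortfall does not depend on it: w = 0.239 uses only the stated proportions, the named test and the allocation ratio.

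**The sums themselves are right.** 29 + 53 is 82, and 82 × 1.2 is 98.4. This also stands. The mistake is sizing the trial with the wrong test, not faulty addition.

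**The chi-square is the least favourable choice.** It ignores the ordering of an outcome that Table 1 calls ordinal, and it gives the lowest power of the two-sided tests considered. This is fair, but it is the test the Protocol names, and the best two-sided alternative reaches only 63% at 98.

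**The framework is unsettled.** Trial design declares equivalence. If that were the real aim, superiority power would not be the relevant figure. This limits what the replacement figures mean but does not rescue the calculation. The sample size section powers for tablets being better and gives no equivalence margin, and 29 + 53 is not a two-arm size under either framework.

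**A statistical analysis plan might deal with it.** It could not make this claim correct, because the 80% is stated in the Protocol and fails on the Protocol's own inputs.

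**Conclusion.** The concern holds. The stated 80% power does not apply to tablets against gum. For the planned chi-square it is about 48% at 82 evaluable, 55% at 98 and 46% with 20% loss. If the assumed difference is real, that test would miss it in about 45% of trials with no loss (100 − 55.2) and about 54% with 20% loss (100 − 45.6). With a rank test on all 98 the figure is about 38%. Reaching 80% with the chi-square takes about 170 evaluable patients, roughly twice 82.

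These figures assume a superiority comparison, a two-sided 5% level, equal arms and the Protocol's proportions. The Protocol gives those proportions for 1 month, while its last visit is at 15 days. Whether they apply at 15 days cannot be judged from the document.

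**What to change.** In III.A 3) Sample size calculation:

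- Delete the two one-arm calculations and their sum.
- State the between-arm effect size, w = 0.239, with the two sets of proportions it comes from.
- Replace the 80% claim with the power of the chi-square at the planned 98: about 55% with no loss and about 46% with 20% loss.
- State that 80% would need about 170 evaluable patients. Allowing for 20% loss, that is 170 / 0.8 = 212.5, so 213 enrolled, or 214 for equal arms.
- Say that these figures are conditional on a superiority test and on the assumed proportions, given the equivalence label in Trial design and the gap between 1 month and 15 days.

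A smaller clarification: raising 82 by 20% to 98 keeps 82 evaluable only if loss is at most 1 − 82/98 = 16.3%.

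The cost is Protocol wording and a less favourable power statement. No extra patients are needed to correct the figure; enrolling enough for 80% would be a separate decision for the sponsor.

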#### **4) Recruitment:**

Patients will be recruited by Y.S from intensive care units in Kasr el Ainy hospitals, Faculty of Medicine, Cairo University, where there is a continuous and high patient flow from which eligible patients will be recruited to fulfill the eligibility criteria .

### **B) Assignment of interventions (Allocation):**

#### **1) Sequence generation:**

Simple randomization will be done by generating numbers from 1:98 using Random Sequence Generator, Randomness and Integrity Services Ltd (<https://www.random.org/>) by Y.S. Each generated random number will represent assigning intervention and comparator in a random manner, i.e.: No. 1 intervention No.2 comparator.

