#### **2) Allocation concealment:**

Operator M.A. will choose between numbers in an opaque sealed envelope, which will be arranged by Y.S. who will not be involved in any of the phases of the clinical trial. Data will be recorded on a computer by M.A. and H.M. and all records of all patients will be kept with the main supervisor A.E.

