### **3) Implementation:**

Y.S. will generate the allocation sequence, enroll participants, and assign participants to interventions.

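### The allocation sections do not guarantee a fixed, auditable order of assignment, and calling the method simple randomization does not secure the planned 49 per group

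*Protocol*

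**What the plan says.** Four parts of the Protocol bear on how a patient reaches an arm.

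- **Sequence generation (III.B.1):** "Simple randomization will be done by generating numbers from 1:98 using Random Sequence Generator". It continues: "Each generated random number will represent assigning intervention and comparator in a random manner", with the key given as "No. 1 intervention No.2 comparator". The other 96 numbers have no stated arm.
- **Allocation concealment (III.B.2):** the operator "will choose between numbers in an opaque sealed envelope". The envelope is arranged by the team member who generates the sequence, and the section says this person has no part in any phase of the trial.
- **Implementation (III.B.3):** that same team member "will generate the allocation sequence, enroll participants, and assign participants to interventions".
- **Planned sizes:** Trial design gives "Allocation ratio: 1:1", and Sample size calculation gives "total of (98) cases i.e. (49) for each group".

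The Participant timeline (Table 2), Recruitment, and Consent or assent sections also give this team member recruitment, consent and randomization.

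**The concern.** Random allocation protects against selection bias only if the order is fixed in advance, must be followed, and is unknown to whoever decides that the next patient enters. Here a random set of numbers is generated, but the step that dispenses them is described as a choice. Since a number stands for an arm, how it is picked matters. If a draw could be repeated, swapped or held for a later patient, nothing in the described procedure would show it. Bias introduced in this way cannot be removed at analysis.

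A lesser issue is that simple randomization places no restriction on the final split, while the Protocol plans equal groups of 49.

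**Working it through.** **1. The allocation text, side by side**

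| Question | Sequence generation | Allocation concealment | Implementation |
|---|---|---|---|
| What does a number mean? | An arm; only Nos. 1 and 2 decoded | Not stated | Not stated |
| Who determines the assignment? | Not stated | The operator, by choosing a number | The sequence generator |
| In what order are numbers used? | Not stated | Not stated | Not stated |
| Is the patient recorded before the number is seen? | Not stated | Not stated | Not stated |
| Is the sequence generator separate from enrolment? | Not stated | Yes, said to be in no phase | No, enrols and assigns |

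The second and fifth rows are contradictions. The third and fourth rows are gaps that the choosing step makes important. The envelope is also written in the singular, so it is unclear whether there is one envelope holding many numbers or one per patient. The Blinding section says the operator is blinded to the material, yet the operator handles numbers that stand for arms.

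**2. The planned sizes**

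The Protocol's figures reproduce. Goodness-of-fit chi-square sizes with 2 degrees of freedom, alpha 0.05 and power 80% are 29 for w = 0.578 and 53 for w = 0.43. Then 29 + 53 = 82, and 82 × 1.2 = 98.4, taken as 98, or 98 / 2 = 49 per group. This confirms the arithmetic only. Whether that sample size method is suitable is a separate question.

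**3. What simple randomization gives with 98 patients**

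The size X of one arm is Binomial(98, 0.5).

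- SD = √98 / 2 = 4.95
- P(X = 49) = C(98, 49) / 2^98 = 0.080
- P(split of 44:54 or more uneven) = 0.363
- P(split strictly more uneven than 44:54) = 0.266
- 2.5% and 97.5% quantiles: 39 and 59; P(more uneven than 39:59) = 0.033

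**4. What the imbalance costs**

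Efficiency relative to an equal split, assuming similar variance in both arms, is 4ab / N².

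- 44:54: 4 × 44 × 54 / 98² = 9504 / 9604 = 0.990, a loss of about 1%
- 39:59: 4 × 39 × 59 / 98² = 9204 / 9604 = 0.958, a loss of about 4%

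**5. The alternative reading**

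If the numbers 1 to 98 are shuffled and each used once, with half keyed to each arm, the split is exactly 49:49 once all 98 are allocated. An odd/even rule extending the key for Nos. 1 and 2 would do this, but that rule is an assumption. The scheme would then be restricted (one block of 98), not simple.

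**The case against.** The strongest reply on the allocation order is that the envelope is opaque and sealed. Someone who draws a number unseen has not chosen an arm, and a blind draw without replacement can be random. The operator is said to be blinded, nothing says the operator holds the key, and re-drawing is nowhere mentioned. The list-holder arranges the envelope, which may imply an order. This stands as far as it goes. A reader might infer that the arm is fully predictable at the draw, or that the generated order can never bind. The Protocol does not support either: predictability would require the operator to see the number, know the key and be free to pick. What remains is that the Protocol neither fixes an order nor creates a record by which adherence to one could be checked.

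On group sizes, the reply is that 49 per group is a planning figure in the sample size section. Simple 1:1 randomization meets it in expectation, and the alternative reading meets it exactly. This also stands. A reader might infer that the Protocol contradicts itself or cannot deliver 49:49, but the text shows only that the named method does not guarantee that split.

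Numbered envelopes alone would also not be enough. If the person who holds the list still enrols patients, the next arm can be foreseen however the envelopes are used.

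**Conclusion.** The point holds in two parts of unequal weight.

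**Main part.** Sequence generation, Allocation concealment and Implementation together do not guarantee a fixed, auditable allocation order. They disagree on who assigns, and on whether the sequence generator is separate from enrolment. This leaves room for selection at allocation; it does not show that selection will happen, and the document gives no basis for a numerical estimate of the bias. It should be settled before the first patient is allocated. The conclusion rests only on what the sections state and omit.

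**Secondary part.** The label is imprecise. Under truly simple randomization, exactly 49:49 occurs in about 8% of trials and a split of 44:54 or worse in about 36%. The efficiency loss is about 1% at 44:54 and 4% at 39:59, so this part alone would be minor. If the numbers are each used once with half keyed to each arm, the split is right and only the name is wrong.

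**What to change.** 1. Delete the wording that has the operator choose between numbers, and the partial key for Nos. 1 and 2.
2. Name the scheme correctly and require a complete list of 98 allocations before recruitment. One example is a restricted computer-generated list with 49 per arm, in permuted blocks of varying size that sum to 98. Keep the list from anyone who enrols or assigns.
3. Place one allocation in each sequentially numbered, opaque, sealed envelope. Open envelopes strictly in order, and only after the patient's study number, date and time have been written on the outside.
4. Reconcile Sequence generation, Allocation concealment, Implementation, Recruitment, the Participant timeline and Consent or assent, so that the team member who holds the list does not enrol or assign. State one person who opens the envelopes, and check that choice against the Blinding section.

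The cost is protocol wording, a new list and a reallocation of tasks within the existing team. No extra patients or staff are needed.

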#### **2) Allocation concealment:**

Operator M.A. will choose between numbers in an opaque sealed envelope, which will be arranged by Y.S. who will not be involved in any of the phases of the clinical trial. Data will be recorded on a computer by M.A. and H.M. and all records of all patients will be kept with the main supervisor A.E.

### **3) Implementation:**

Y.S. will generate the allocation sequence, enroll participants, and assign participants to interventions.

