##### **2) Eligibility criteria:**

###### **a- Eligibility criteria of participants :**

- **Inclusion Criteria :**

- (1) Age range above 65 years old
- (2) Bedridden patients
- (3) Males or females
- (4) Conscious patients
- (5) Co-operative patients approving to participate in the trial.
- (6) Subjects who signed informed consent

- **Exclusion criteria:**

- (1) Individuals had taken antibiotics during the last four weeks or anticipated doing so during the study
- (2) Subjects who wore removable prosthesis
- (3) Patients with systemic diseases that have any oral manifestations
- (4) History of Smoking
- (5) Allergy to any of chewing gum or tablets ingredients
- (6) Evidence of temporomandibular joint disorders
- (7) Presence of intraoral infections
- (8) Currently using any mouth rinse

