## **C) Data collection, management, and analysis:**

### **1) Data collection methods:**

#### **1.1. Baseline data collection:**

For every patient medical and dental history will be taken. Examination charts will be filled by Y.S.

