#### **1.3. Patient retention:**

The phone number of the patient or his/her caregiver will be recorded in the patient's chart. The patient will receive a phone call by Y.S. to remind him of the time of the operator M.A. visit for saliva and plaque sampling. Moreover, patients will receive a daily phone message in the time assigned for chewing either the gum or the tablet.

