### **3) Consent or assent:**

Y.S. is responsible of admitting and signing the informed consents during enrollment day.

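### The person whose non-involvement is meant to protect allocation concealment also generates the sequence, recruits, takes consent and randomizes, so concealment from the enroller is not secured

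*Protocol*

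**What the plan says.** All references are to the Protocol; the people concerned are identified here by role.

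- **III.B Sequence generation:** the recruiter generates a simple random sequence of the numbers 1 to 98. The section links number 1 to the intervention and number 2 to the comparator.
- **III.B Allocation concealment:** the operator "will choose between numbers in an opaque sealed envelope". The envelopes are arranged by the recruiter, described here as someone "who will not be involved in any of the phases of the clinical trial".
- **III.B Implementation:** the recruiter "will generate the allocation sequence, enroll participants, and assign participants to interventions".
- **III.A Participant timeline (Table 2):** recruitment, diagnosis, consent, baseline data collection and randomization are all assigned to the recruiter, all at T0.
- **III.A Recruitment:** "Patients will be recruited by" this same person.
- **III.C Baseline data collection:** "Examination charts will be filled by" the recruiter.
- **III.C Patient retention:** "The patient will receive a phone call by" the recruiter, as a reminder of sampling visits.
- **IV Consent or assent:** the recruiter "is responsible of admitting and signing the informed consents during enrollment day".
- **III.B Blinding:** the operator and the two assessors are said to be blinded to the material.
- **III.D Data monitoring:** the main supervisor watches for bias arising from participants, operator or assessors. The recruiter is not named.

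**The concern.** Allocation concealment requires that whoever decides whether a patient enters the trial can neither know nor infer the next allocation. The Protocol relies partly on the envelope-arranger standing outside the trial, then gives that person the whole enrolment pathway. It also describes two allocation procedures that staff cannot both follow.

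Several eligibility criteria leave room for judgment, for example "Co-operative patients approving to participate in the trial", whether the patient is conscious, and whether antibiotics are anticipated during the study. If the enroller knows or can guess the next arm, these criteria allow patients to be steered towards or away from it. Blinded colony counting, blinded assessors and a pH meter protect the measurements. They do not protect the make-up of the two groups, and no analysis can reliably undo selective entry once patients are enrolled.

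**Working it through.** The Protocol gives no figure to reproduce here, so the check is a count and a side-by-side reading.

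**1. Count of Table 2 rows by person**

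| Activity | Assigned to |
|---|---|
| Recruitment | Recruiter (also the envelope-arranger) |
| Diagnosis | Recruiter |
| Consent | Recruiter |
| Baseline data collection | Recruiter |
| Randomization | Recruiter |
| Saliva and plaque sampling | Operator |
| Outcome assessment | Two assessors |

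Recruiter: 5 of 7 = 71%. Operator: 1 of 7. Assessors: 1 of 7. If the randomization row is read as no more than preparing envelopes, and so as compatible with the Allocation concealment section, 5 − 1 = 4 of 7 rows still contradict it.

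**2. Is it a slip in one place?** Seven places give this person a trial role: Table 2, Recruitment, Sequence generation, Implementation, Baseline data collection, Patient retention, and Consent or assent. Only Allocation concealment says the person has none.

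**3. Who allocates?**

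| Source | Who allocates |
|---|---|
| Allocation concealment | The operator picks a number from an envelope |
| Implementation | The recruiter assigns |
| Table 2 | The recruiter randomizes |

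Nothing says which governs.

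**4. Would the operator's draw be enough to hide the allocation from the recruiter?** It would need three conditions:

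- The recruiter cannot tell which envelope comes next. The recruiter arranges the envelopes, and no fixed order of use is set.
- Enrolment is final before the draw. Consent, randomization and baseline sampling all sit at T0 with no stated order.
- The draw takes precedence over Implementation and Table 2. No section says so.

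**5. How many allocations could the enroller know beforehand?** This depends on assumptions, because the Protocol does not settle the procedure.

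- Operator draws from envelopes that cannot be told apart: 0 of 98.
- Recruiter assigns from the list that the recruiter generated (assuming the list is in view): 98 of 98.

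This range describes the ambiguity. It is not an estimate of bias.

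**6. Secondary point: operator blinding.** The operator picks the number, and Sequence generation links numbers to arms, although only numbers 1 and 2 are spelled out. The operator also samples at T1, 5 minutes after use of two visibly different products: a gum chewed for 5 minutes, or a tablet that is chewed, swished and swallowed. The Blinding section does not say how the operator stays blinded.

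**The case against.** The strongest defence is that Allocation concealment offers more than the arranger's non-involvement. It also specifies opaque sealed envelopes and a draw by the operator, who has no recruitment, diagnosis or consent role. On that reading the recruiter prepares and administers while the operator's draw separates allocation from enrolment, and the sections can live together. It can be added that preparing the sequence is the envelope-arranger's natural task, that baseline charts and reminder calls have no bearing on concealment, that most eligibility criteria are factual (age, prosthesis, smoking, recent antibiotics), and that the supervisors' audit of research methods could cover allocation.

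Part of this stands. Non-involvement is one of several stated safeguards, the 5-of-7 count shows how pervasive the contradiction is and not how serious, and the 0-to-98 range is conditional. It is also fair that the Protocol does not state that the operator decodes the number or watches the product being used, so the operator-blinding point is an inference and secondary.

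The core is untouched. The harmonized reading needs the three conditions in step 4 above, and the Protocol states none of them. A few judgment-based criteria are enough for selective entry, and a general audit does not hide the next allocation from the person who made the list.

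**Conclusion.** The concern holds. The Protocol contradicts itself on whether the envelope-arranger takes part in the trial and on who allocates, and as written it does not secure concealment from the enroller. This does not say that bias has occurred, and its size cannot be derived from the document. The conclusion rests only on the Protocol's own role assignments; the upper end of the 0-to-98 range additionally assumes that the recruiter assigns from the self-generated list. It must be fixed before enrolment starts, because selective entry cannot be corrected later. The operator-blinding claim is unsupported as worded but matters less, since colonies are counted by an examiner unaware of treatment, the assessors are blinded and pH is read by a meter.

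**What to change.** **Essential**

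- In Sequence generation, Allocation concealment and Implementation, name an existing team member who does not enrol, sample or assess to generate the sequence and prepare sequentially numbered, opaque, sealed envelopes. If a co-supervisor takes this on, another supervisor should audit allocation, because Auditing makes the supervisors the auditors.
- Have the recruiter enrol and take consent without access to the sequence or the envelope contents.
- State that envelopes are opened strictly in order and only after consent and T0 sampling, and name one person who opens them. Someone other than the recruiter and the sampling operator is best: this keeps allocation separate from enrolment without telling the operator the arm.
- Bring Table 2 and Recruitment into line with this.

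**Minor**

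- Extend the bias monitoring in Data monitoring to enrolment and allocation.
- In Blinding, delete the operator claim or say how it is achieved, and keep the blinded assessors.

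**Cost:** reassignment of tasks among people already named, and wording changes in Table 2, Recruitment, the four III.B sections and Data monitoring. Sample size, treatments, outcomes and analysis are unaffected. The team must first confirm who is free of enrolment, sampling and assessment duties, since the Protocol does not state this for the co-supervisors.
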